### 9.2 Missing Data Approach

Missing data mechanisms will be examined by comparing completers with incompleters on the baseline factors. Multiple imputation (SAS proc mi and mianalyze) will be used if a substantial amount ( $>10\%$ ) of missing data exist. If differential missing patterns are observed, sensitivity analyses will be performed to evaluate the consequences of potential missing mechanisms.

### 9.3 Potential Moderators, including Biological Sex, of Intervention Effects

In exploratory analyses, we will test interactions between the following baseline factors and treatment group to examine these factors as potential moderators of intervention effects: age, sex, inflammation biomarkers levels, ISI scores, PHQ-9 and SCL-20 scores, use of sleep aids/medications, and nonprescription substance use. Given that the proposed trial is not powered to detect such interactions, specific models will also be run separately for males and females to assess whether there are clinically important differences in the treatment group-outcome relationships between sexes.

#### 9.4 Mediation Analyses

Preliminary mediation analyses to assess for intervention-related decreases in ISI scores, behavioral changes, and HIV virologic rebound (either singly or in combination) to explain reductions in the inflammation/monocyte activation endpoints will be performed.

#### 9.5 Sample Size Justification

The goal of this application is to provide proof-of-concept data and effect sizes of SHUTi on inflammation/monocyte activation endpoints in support of a future, definitive trial. As such, the proposed sample size is based on the enrollment time period and the funding allowance of the R21 mechanism, not for definitive superiority testing. We will enroll 50 participants with the expectation that 40 (20 in each arm) will complete the 24 week study. Using the standard deviations and correlations between baseline and week 24 for hsCRP (this trial's primary endpoint) from our previously published depression trial, we have 80% power ( $\alpha=0.05$ ) to detect mean differences between study groups of 3.41 mg/L. This detectable difference is clinically meaningful, as it is similar to that found to be predictive of CVD events and overall mortality in the SMART trial (66, 110).

For the primary and secondary endpoints, the following table demonstrates the effect sizes that can be observed between study groups (N=20 in each arm), assuming similar variances and correlations as observed in our pilot trial of internet CBT for depression in PWH. Of note, the detectable difference in IL-6 is also clinically meaningful, given that differences of 1.3-2.2 pg/mL were associated with greater risks of CVD and mortality in the SMART trial (66, 110).

Outcome	SD	Correlation	Detectable mean difference (N=20 per group)
hsCRP (mg/L)	4.87	0.64	3.41
IL-6 (pg/mL)	2.34	0.32	2.02
sCD14 (ng/mL)	751	0.70	488
sCD163 (ng/mL)	19.12	0.89	7.97
%CD14+CD16+ monocytes	5.54	0.31	4.77

Our group has access to ~3000 HIV-positive outpatients engaged consistently in care within the Indiana University Health system (Eskenazi Health with 1200; IU Methodist Hospital with 1800). As part of our pilot trial, we found that ~30% of the virologically-suppressed PWH in our HIV clinics have ISI scores  $\geq 11$ . Thus, there are ~900 patients eligible for recruitment. Based on review of our clinic population characteristics, we estimate ~800 will fulfill the other eligibility criteria.

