This single-center, phase II RCT evaluating the effect of Sleep Healthy Using The Internet (SHUTi), on systemic inflammation in PWH is highly significant for several reasons: (1) A positive phase II trial would generate the critical proof-of-concept data and effect size estimates needed to justify and properly design a multicenter, phase III RCT to establish the long-term effects of SHUTi on systemic inflammation and SNAE. As we have ongoing relationships with the AIDS Clinical Trials Group, implementing such a trial is feasible in our hands. (2) A positive phase III trial would identify a novel target (insomnia) for SNAE prevention efforts and would suggest that clinical management guidelines for PWH should, for the first time, include insomnia screening and treatment to improve physical health outcomes. (3) A positive phase III trial would also equip healthcare systems with a new practical and scalable intervention (SHUTi) to help lower SNAE risk. Importantly, SHUTi avoids drug dependence and drug interaction concerns associated with some pharmacologic therapies for insomnia and does not rely on mental health specialty providers trained in CBT-I, which are in short supply. Thus, given the high prevalence of insomnia in PWH, this application may lead to widespread, clinically relevant changes to improve the lives of PWH.

**2.2.2 Insomnia, Inflammation, and Chronic Diseases in the General Population.** *Insufficient sleep* is a highly prevalent and harmful health behavior that contributes to poor mental and physical health outcomes (22). Here, insufficient sleep is defined as the presence of insomnia – frequent and persistent difficulty in initiating or maintaining sleep causing functional impairment or distress (23-25). A 2006 Institute of Medicine report (26) stated that promoting *sufficient sleep* may alter the adverse mental and physical health aging trajectories of vulnerable adults.

Insomnia is the most prevalent sleep disorder and is a major public health concern (27). Insomnia afflicts millions of U.S. adults, with 12-20% having insomnia disorder (28, 29) and 30-50% having insomnia symptoms (30, 31). Insomnia is typically chronic (32, 33), and its serious ramifications include absenteeism and accidents (34); the development of psychiatric disorders (35); the development of chronic diseases, (including diabetes, cardiovascular disease, and dementia) (36-42); and high total annual costs (43, 44).

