**2.3.2 CBT for depression in PWH improves measures of inflammation.** We have now published our pilot trial of 54 PWH on virologically-suppressive ART with PHQ-9 scores  $\geq 10$  (indicating high likelihood of a depressive disorder) who were randomized 1:1 to either the use of an internet CBT program for depression (Beating the Blues-US™ (BtB), N=27), which includes 8 weekly treatment sessions, or Usual Care (UC, N=27) (93). Three and two participants, respectively, were lost to follow-up over 24 weeks (9% overall attrition). There were no restrictions on use of depression therapies (pharmacologic or behavioral) nor on types of ART regimens. We found that BtB significantly reduced PHQ-9 scores over 24 weeks compared to UC, indicating persistent BtB effects well beyond the initial treatment period. Moreover, the intervention significantly reduced sCD163 levels and proportions of pro-inflammatory, intermediate CD14+CD16+ monocytes (Table 1). The intervention also led to non-significantly greater reductions in hsCRP, IL-6, and sCD14 levels. Overall, these data strongly suggest that internet CBT treatment of a mood disorder can directly improve markers of systemic inflammation and monocyte immune activation in PWH.

Table 1. Comparison of mean (SD) changes from Entry to Week 24 in depression scores and inflammation/monocyte activation biomarkers between Usual Care (UC) and the Beating the Blues (BtB) study group.

Changes in Endpoint from Entry to Week 24	UC	BtB	Difference BtB vs. UC (95% CI)	P-value
PHQ-9	-1.38 (5.00)	-6.00 (6.60)	-4.63 (-8.00, -1.25)	0.008
hsCRP (mg/L)	0.92 (4.79)	-0.26 (2.55)	-1.18 (-3.50, 1.14)	0.33
IL-6 (pg/mL)	0.56 (2.36)	-0.24 (2.31)	-0.80 (-2.24, 0.64)	0.27
sCD14 (ng/mL)	118 (406)	-134 (571)	-251 (-561, 579)	0.11
sCD163 (ng/mL)	4.71 (9.96)	-1.36 (5.88)	-6.07 (-11.03, -1.11)	0.024
%CD14+CD16+ monocytes	2.23 (6.42)	-1.84 (6.15)	-4.07 (-7.72, -0.42)	0.030

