## 2.4 Study Rationale

The extant literature indicates that insomnia is a risk factor for chronic disease in the general population. Moreover, our published data suggests this relationship holds in PWH, as having highly bothersome insomnia symptoms is associated with incident CVD in PWH. There is strong and rigorous evidence that insomnia is associated with greater levels of systemic inflammation and that treatment of insomnia using CBT-I reduces hsCRP levels in the general population. Similarly, our published pilot trial suggests that treatment of depression using internet CBT reduces systemic inflammation and monocyte activation in PWH. Finally, our small pilot trial indicates that use of internet CBT-I (SHUTi) in PWH reduces insomnia symptoms as measured by ISI scores. What remains unknown is whether treating insomnia with internet CBT-I improves systemic inflammation in PWH. Thus, this trial will fill this critical knowledge gap in preparation for a definitive, end-point driven multicenter RCT of SHUTi on SNAE.

*Our long-term goal is to reduce the risk of SNAE in adult PWH.* The central objective of this study is to evaluate SHUTi's ability to reduce systemic inflammation, and, in particular, monocyte activation in PWH. A positive phase II trial would provide the proof-of-concept data and effect size estimates needed to justify and properly design an R01-funded phase III RCT to establish the long-term effects of SHUTi (a practical and readily scalable intervention) on HIV-related inflammation and prevention of SNAE.

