## 5.2 The Active Control Group: Internet Sleep Education/Hygiene, Symptom Monitoring, and Usual Care.

In our pilot trial, our comparator was usual care. However, in the proposed trial, we will use an active control comparator (107) for two reasons. First, we wish to obtain precise effect size estimates for the next-step trial, and a usual care comparator could overestimate efficacy. Of note, Irwin's RCT (21) found moderate-to-large improvements in insomnia remission and CRP with CBT-I versus a sleep education/hygiene active control. Second, our active control arm will help to ensure that the groups have similar expectancy of benefit.

The Active Control RA, another clinical psychology PhD mentee of [name], will oversee and deliver the active control procedures. First, the RA will give participants access to the internet sleep education/hygiene program, which was created by our consultant, [name], to serve as a standardized active control condition for SHUTi. This educational program was developed at the University of Virginia with funding from the National Institutes of Health and is fully accessible via tablets and smartphones. This program provides static information about: insomnia symptoms; the impact, prevalence, and causes of insomnia; when to see a doctor; and basic lifestyle, environmental, and behavioral strategies to improve sleep (i.e., sleep hygiene recommendations). Of note, participants in our trial will not enter any identifying information into the internet sleep education/hygiene program other than the email address they choose to use to receive messages (e.g., reminders) from the program. The content for this program was informed based on a review of insomnia-focused websites at the time of development. Second, just after giving participants access the internet sleep education/hygiene program, the RA will email or mail a list of local behavioral health services to patients and will encourage them to follow-up with their HIV provider. To engender expectancy of benefit, the RA will stress that our notifications should prompt actions by their provider and that the available treatments are evidence-based. We will then notify the HIV provider, which will encourage them to address their patient's

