## 9.0 STATISTICAL CONSIDERATIONS AND DATA MANAGEMENT

### 9.1 General Considerations

To test our hypotheses, we will use intention-to-treat (ITT) analysis of covariance models to test for treatment group differences in Week 24 levels of inflammation biomarkers adjusted for baseline levels. P-values will be two-sided and considered significant at  $\alpha=0.05$ . Adjustments for multiple comparisons will not be performed due to the relatively small sample size and exploratory nature of this phase II trial.

In secondary/exploratory analysis, multivariable linear regression models will be constructed to include treatment group and other potentially confounding baseline and time-updated variables that differ significantly between groups and which may account for differences in outcomes. Baseline characteristics that may be included in the models are demographics (age, sex, race/ethnicity), ISI scores, PHQ-9 and SCL-20 scores, tobacco/adherence questionnaire results, ART drugs/regimens (including efavirenz, rilpivirine, and integrase inhibitors), insomnia medication use, comorbidities, CD4 cell counts, HIV-1 RNA levels, levels of the inflammation biomarkers, and nonprescription substance use. Time-varying characteristics that may be included are changes in ISI scores, questionnaire results, CD4 cell counts, ART drugs/regimens, and HIV-1 RNA levels.

We will also perform ‘per protocol’ secondary analyses comparing the ISI4-6 subgroup (defined as participants who completed  $\geq 4$  of the 6 SHUTi sessions) vs. the active control group to determine if greater SHUTi engagement leads to greater differences in the endpoints of interest.

We will also examine relationships between changes in questionnaire scores, especially ISI scores, and the inflammatory endpoints using Pearson correlations.

All of these models will be repeated for comparing 12-week changes in the endpoints in addition to the primary models for 24-week changes.

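### Does a trial whose stated product is an effect size need an expected precision for hsCRP, and not only power at 3.41 mg/L?

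*Protocol*

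**What the plan says.** Protocol 9.5 and the matching SAP paragraph on sample size give the purpose: "The goal of this application is to provide proof-of-concept data and effect sizes of SHUTi on inflammation/monocyte activation endpoints", in support of a later definitive trial. The number of participants is attributed to the enrolment period and the funding mechanism, "not for definitive superiority testing". Fifty are randomised and 40 (20 per arm) are expected to complete. The quantitative support is 80% power at a 3.41 mg/L difference in hsCRP and a table of detectable differences for five biomarkers, "assuming similar variances and correlations as observed in our pilot trial of internet CBT for depression in PWH".

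Four other places bear on the point.

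- Protocol 9.1 and the SAP (Statistical Analyses) plan an intention-to-treat ANCOVA of Week 24 levels adjusted for baseline. On inference they say "P-values will be two-sided and considered significant at" the 0.05 level. Neither mentions a confidence interval.
- Protocol 2.2.1 and 2.4 look ahead. In 2.4: "A positive phase II trial would provide the proof-of-concept data and effect size estimates needed to justify and properly design" the next trial.
- Protocol 5.2 explains the choice of an active control: "we wish to obtain precise effect size estimates for the next-step trial, and a usual care comparator could overestimate efficacy".
- Protocol 2.3.2, Table 1, gives the hsCRP result of the depression trial that supplied the SD and correlation: -1.18 mg/L (95% CI -3.50 to 1.14, P=0.33).

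**The concern.** A trial justified by estimation would normally say how well it will estimate. This plan answers a different question, what it could detect, and leaves out the interval width. Once worked out, the width is not flattering: a half-width of 2.4 mg/L is twice the only randomised 24-week hsCRP difference in people with HIV that the documents print, and no narrower than the interval around that earlier result.

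The stake would be the next trial. Suppose the true difference were near 1.18 mg/L, progression depended on p<0.05, and phase III were sized on the estimate that passed that filter. Significant results would then be rare, and those that occurred would overstate the effect about 2.5-fold. A phase III trial planned on such an estimate would be far too small. Conversely, a non-significant result might be read as a failure while its interval still covered a worthwhile effect.

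**Working it through.** **Inputs.** SD 4.87 mg/L, correlation 0.64 and 20 completers per arm (Protocol 9.5, SAP); two-sided alpha 0.05 and ANCOVA on baseline (Protocol 9.1, SAP); difference -1.18 with limits -3.50 and 1.14 (Protocol Table 1).

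**Reproducing 3.41 mg/L.**

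- Residual SD = 4.87 × √(1 − 0.64²) = 3.742 mg/L.
- SE = 3.742 × √(2/20) = 1.183 mg/L, with 40 − 3 = 37 degrees of freedom.
- Noncentral t: detectable difference at 80% power 3.40 mg/L; power at 3.41 is 80.1%. The plan's figure is right.
- The same formula gives 2.02, 488, 7.93 and 4.79 for the other four rows, against printed values of 2.02, 488, 7.97 and 4.77.

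**Expected precision from the same inputs.**

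- 20 per arm: 2.026 × 1.183 = 2.40 mg/L.
- 25 per arm: SE = 3.742 × √(2/25) = 1.058; 2.012 × 1.058 = 2.13 mg/L.
- Depression trial: (3.50 + 1.14)/2 = 2.32 mg/L.
- Ratios to 1.18: 2.40/1.18 = 2.03 and 2.13/1.18 = 1.80.
- With 20 per arm and assumed ranges (SD 3.5 to 6.0, correlation 0.5 to 0.8): 1.35 to 3.33 mg/L.

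At 20 per arm the detectable difference is 3.41/2.40 = 1.42 times the half-width. The printed table therefore already carries the precision information: dividing a row by 1.42 gives that row's half-width. For IL-6, 2.02/1.42 = 1.42 pg/mL.

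**The harm scenario and what it depends on** (20 per arm; significant estimates in the right direction, by simulation):

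| Assumed true difference (mg/L) | Power | Mean significant estimate ÷ truth |
|---|---|---|
| 1.18 | 16% | 2.48 |
| 2.4 | 51% | 1.38 |
| 3.41 | 80% | 1.12 |
| 3.9 | 89% | 1.06 |

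At a true 1.18 the mean significant estimate is 2.93 mg/L. A later trial planned on 2.9 mg/L with 80% power and the same SD and correlation would analyse 28 per arm and have 21% power at 1.18, where 159 per arm are needed.

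The alarming figures belong to the first row only. The plan does not adopt that row. Protocol 3.1 bases the hsCRP endpoint on the CBT-I trial in HIV-negative adults, and 5.2 describes that trial's gains in remission and CRP over a sleep-education control as moderate to large. If that is read as 0.5 to 0.8 SD (my assumption), the difference is 0.5 × 4.87 = 2.4 to 0.8 × 4.87 = 3.9 mg/L. The inflation is then modest.

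**The other two links.** *Positive*, in 2.2.1 and 2.4, is prose about significance and rationale; no decision rule is attached to it there or in Section 9. On phase III, 2.4 describes an end-point driven multicentre trial on serious non-AIDS events, and 2.2.1 names inflammation together with those events. Neither says that its size would come from a significant hsCRP difference.

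**The case for a change.** The strongest case for a change is that the disclaimer about superiority makes matters worse: it names estimation as the purpose, and estimation is exactly what lacks a stated precision. Neither document promises a confidence interval, and with *positive* undefined, p<0.05 is the only criterion a reader can find. The plan borrows the depression trial's variance without mentioning its estimated effect in the sample size section. The remedy would be a few sentences, with no more patients or assays.

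The factual part stands: no half-width is printed, no interval is promised, and even the most favourable assumed inputs give a half-width of 1.35 mg/L, above 1.18. The inference does not. The 1.18 mg/L comes from CBT for depression against usual care, a comparator that 5.2 itself says could overestimate efficacy, so it is a reference point and not an expected SHUTi effect. An analyst who fits the planned ANCOVA obtains the adjusted difference, its standard error and its interval in one step, and this team's earlier trial reported differences with 95% intervals in Table 1. Nothing suggests they would report a bare P-value here. In 5.2, *precise* argues for the choice of comparator, which is a matter of bias and not of interval width.

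**Conclusion.** No change is needed. The plan omits a derived figure; it contains no error. The stated power is correct, the sample size is openly a matter of time and funding, and the half-width of about 2.4 mg/L (2.1 if all 25 per arm contribute) can be read off printed inputs. Stating it would change neither the sample size, the model nor the result reported. A progression rule for phase III would be a design preference, since the documents tie no decision to p<0.05.

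The half-widths assume untransformed hsCRP, the plan's SD and correlation, and either 20 or 25 analysed per arm. A transformation or nonparametric test under Protocol 9.13.2 would change the scale. The conclusion does not depend on these figures. It rests on the planned analysis already producing the interval, and on the harm scenario needing an effect size, a decision rule and a phase III sizing method that the documents do not contain.

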#### 9.6 Criteria for Stopping the Study

No early stopping rule will be implemented.

#### 9.7 Patient Characteristics and Significant Protocol Violations

Demographic and other baseline data will be summarized descriptively for all patients in the ITT set. Comparisons between the two groups will be performed using Pearson's chi-square tests and Student's t-tests. Significant protocol violations will be documented.

## 9.8 Disposition

The number of enrolled subjects will be summarized in a flow chart with frequency of completion and discontinuation. The subjects discontinued from SHUTi and their corresponding information will be listed. Significant protocol violations will be tabulated and/or listed.

## 9.9 Adherence

Adherence status will be tabulated for both arms.

## 9.10 Analysis Datasets

Intent-to-treat set will include patients as randomized regardless their adherence status and data completeness.

Per-protocol set will include patients with 24-week hsCRP measurements and who completed at least 4 out of 6 SHUTi sessions.

## 9.11 Interim Analysis

No interim analysis will be performed.

## 9.12 Subgroup Analysis

Our analyses will be repeated comparing the Active Control group with the SHUTi intervention group who complete  $\geq 4$  of the 6 planned treatment sessions (the SHUTi4-6 subgroup).

## 9.13 Data Management

### 9.13.1 Data Management Systems.

IU REDCap will be used to capture demographics, vital signs, medications, medical/psychologic history, diagnoses, interview, survey, and EHR data. The following IU REDCap databases will be created: Recruitment and Screening, SHUTi Intervention Delivery, Active Control Delivery, Screening Visit, Entry Visit, Week 12 Visit, and Week 24 Visit. Data will be exported from IU REDCap in SAS format. Assay data from the Translation Core Analyte Laboratory (hsCRP, IL-6, sCD14, sCD163) and the Angio BioCore (CD14+CD16+ intermediate monocytes) will be converted from Excel to SAS format and merged with the IU REDCap data.

### 9.13.2 Methods of Data Cleaning

Data cleaning procedures will assess for out-of-range values, outliers, normality, and very low frequency classes for each variable using SAS statistical software. Frequencies will be examined to identify out-of-range (i.e., impossible) values. Identified out-of-range values will be checked against the source data and corrected (any data entry, coding, or computational errors will be fixed and/or assays will be rerun, as appropriate).

scores ( $\leq -3.3$  or  $\geq 3.3$ ) for all continuous variables will be computed to identify outliers. Identified outliers will be checked against the source data and corrected if due to data entry errors. If not due to data entry errors, these values will be noted, retained in primary analyses, and may be altered or removed in sensitivity analyses. Skew ( $\leq -3$  or  $\geq 3$ ) and kurtosis ( $\leq -10$  or  $\geq 10$ ) values will be examined to assess normality of continuous variables. If the normality assumption is not met, variable transformations to normalize distributions and/or distribution-free nonparametric tests for the primary analyses will be considered.

